Treatment Indication(s)	
 • For the treatment of schizophrenia. • Adjunctive therapy to antidepressants for the treatment of major depressive disorder (MDD) 		
Objective(s)	To provide post marketing surveillance data on the safety and efficacy of Brexpiprazole (Rexulti™) Film-coated Tablet for schizophrenia and adjunctive therapy of major depressive disorder (MDD) in the Philippines.		
Study Design			
Center	Multi-center		
Blinding	Open		
Control	Active		
Design	Single Group		
Subject Population			
Planned # of subject	A total of 300 subjects will be included in the trial.		
Gender	Male and Female		
Age range	Adults (18 years old and above)		
Healthy subjects or treatment condition	Treatment condition		
Test Product, Dose, Mode of Administration			
Brand name (API)	Rexulti™	Administration route	Per Orem (PO)
Dosage form	Film-coated Tablet	Dose, regimen	Once a day
Criteria for Evaluation			
Primary Outcome Variables	Safety Assessment: Safety of Brexpiprazole (Rexulti™) Film-coated Tablet will be evaluated based on the reported AE's per assessment.		
Secondary Outcome Variables	Efficacy Assessment: Efficacy of Brexpiprazole (Rexulti™) Film-coated Tablet will be evaluated using the Clinical Global Impression (CGI) Scale : CGI – Severity - Numbers and proportions of responders (defined as patients with CGI severity (CGI-S) score of 1 (normal, not at all ill), 2 (borderline mentally ill), 3 (mildly ill), 4 (moderately ill), 5 (markedly ill), 6 (severely ill), 7 (among the most extremely ill patients)) CGI – Improvement - Numbers and proportions of responders (defined as patients with CGI improvement (CGI-I) score of 1 (very much improved), 2 (much improved), 3 (minimally improved), 4 (no change), 5 (minimally worse), 6 (much worse), 7 (very much worse))		
Study Duration			
Treatment duration	8 weeks		
Further Study Details			
Assessments will be done upon initiation, (Baseline visit), 4 weeks later (Visit 2), until completion of the study week 8 (Study Completion). Demographic information and vital signs will be collected.			

INTRODUCTION

Schizophrenia is a serious mental disorder in which people interpret reality abnormally. Schizophrenia may result in some combination of hallucinations, delusions, and extremely disordered thinking and behavior that impairs daily functioning, and can be disabling. Depression is a mood disorder that causes a persistent feeling of sadness and loss of interest. It is also called as major depressive disorder or clinical depression which affects how you feel, think and behave and can lead to a variety of emotional and physical problems.¹

Brexpiprazole (Rexulti™) is used to treat the symptoms of schizophrenia. It is also used with an antidepressant to treat depression when symptoms cannot be controlled by an antidepressant alone. Brexpiprazole (Rexulti™) is an atypical antipsychotics or second generation antipsychotics. It works by changing the activity of certain natural substances in the brain.

Brexpiprazole (Rexulti™) has partial agonist activity at serotonergic 5-HT_{1A} and dopaminergic D₂ receptors, as well as antagonist activity at serotonergic 5-HT_{2A} receptors. The drug also has activity at noradrenergic receptors. It is available as tablets in the following strengths: 0.25, 0.5, 1, 2, 3, and 4 mg under the brand name Rexulti™.

For schizophrenia, the proposed starting dose is 1 mg once daily for 4 days, increasing to 2 mg for 3 days, and then 4 mg once daily (after Day 7) based on clinical response and tolerability. For adjunctive treatment of major depressive disorder (MDD), the proposed starting dose is 0.5 or 1 mg once daily, increasing to a target dose of 2 mg once daily based on clinical response and tolerability.

The main objective of developing this post marketing surveillance is to monitor the safety and efficacy of the drug in the treatment of schizophrenia and major depressive disorder. Another objective is to enhance their chance for early recovery, eventual reintegration to the society and improved quality of life.

Efficacy and tolerability of Brexpiprazole (Rexulti™) Film Coated Tablet

For the treatment of Schizophrenia

The efficacy of Brexpiprazole (Rexulti™) in the treatment of adults with schizophrenia was demonstrated in two 6-week, randomized, double-blind, placebo-controlled, fixed-dose clinical trials in patients who met DSM-IV-TR criteria for schizophrenia.

In both studies, Study 231 (hereafter “Study 3”) and Study 230 (hereafter “Study 4”), patients were randomized to Brexpiprazole (Rexulti™) 2 or 4 mg once per day or placebo. Patients in the Brexpiprazole (Rexulti™) groups initiated treatment at 1 mg once daily on Days 1 to 4. The

Brexpiprazole (Rexulti™) dosage was increased to 2 mg on Days 5 to 7. The dosage was then either maintained at 2 mg once daily or increased to 4 mg once daily, depending on treatment assignment, for the 5 remaining weeks.

The primary efficacy endpoint of both trials was the change from baseline to Week 6 in the Positive and Negative Syndrome Scale (PANSS) total score. The PANSS is a 30-item scale that measures positive symptoms of schizophrenia (7 items), negative symptoms of schizophrenia (7 items), and general psychopathology (16 items), each rated on a scale of 1 (absent) to 7 (extreme); the total PANSS scores range from 30 (best) to 210 (worst).

In Study 3, Brexpiprazole (Rexulti™) at both 2 mg/day and 4 mg/day was superior to placebo on the PANSS total score. In Study 4, Brexpiprazole (Rexulti™) 4 mg/day was superior to placebo on the PANSS total score (Table 12). Figure 5 shows the time course of response based on the primary efficacy measure (change from baseline in PANSS total score) in Study 3.

Examination of population subgroups based on age, gender and race did not suggest differential responsiveness.

Table 12: Summary of Efficacy Results for Studies in Schizophrenia

[figure not shown]
Study	Treatment Group	N	Primary Efficacy Measure: PANSS		
			Mean Baseline Score (SD)	LS Mean Change from Baseline (SE)	Placebo-subtracted Difference ^a (95% CI)
3	REXULTI (2 mg/day)*	180	95.9 (13.8)	-20.7 (1.5)	-8.7 (-13.1, -4.4)
	REXULTI (4 mg/day)*	178	94.7 (12.1)	-19.7 (1.5)	-7.6 (-12.0, -3.1)
	Placebo	178	95.7 (11.5)	-12.0 (1.6)	--
4	REXULTI (2 mg/day)	179	96.3 (12.9)	-16.6 (1.5)	-3.1 (-7.2, 1.1)
	REXULTI (4 mg/day)*	181	95.0 (12.4)	-20.0 (1.5)	-6.5 (-10.6, -2.4)
	Placebo	180	94.6 (12.8)	-13.5 (1.5)	--

SD: standard deviation; SE: standard error; LS Mean: least-squares mean; CI: unadjusted confidence interval.

* Dosages statistically significantly superior to placebo.

^a Difference (drug minus placebo) in least-squares mean change from baseline.

Figure 5: Change from Baseline in PANSS Total Score by Study Visit (Week) in Patients with Schizophrenia in Study 3

[figure not shown]
The safety and efficacy of Brexpiprazole (Rexulti™) as maintenance treatment in adults with schizophrenia aged 18 to 65 years were demonstrated in the maintenance phase of a randomized withdrawal trial (Study 331-10-232, hereafter “Study 5”). Patients were stabilized for at least 12 weeks on 1 to 4 mg/day of Brexpiprazole (Rexulti™) (N=202). They were then randomized in the double-blind treatment phase to either continue Brexpiprazole (Rexulti™) at their achieved stable dose (N=97), or to switch to placebo (N=105).

The primary endpoint in Study 5 was time from randomization to impending relapse during the double-blind phase, defined as: 1) CGI-Improvement score of ≥ 5 (minimally worse) and an increase to a score > 4 on PANSS conceptual disorganization, hallucinatory behavior, suspiciousness, or unusual thought content items, with either a ≥ 2 increase on a specific item or ≥ 4 point increase on the combined four PANSS items, 2) hospitalization due to worsening of psychotic symptoms, 3) current suicidal behavior, or 4) violent/aggressive behavior.

A pre-specified interim analysis demonstrated a statistically significantly longer time to relapse in patients randomized to the Brexpiprazole (Rexulti™) group compared to placebo-treated patients. The trial was subsequently terminated early because maintenance of efficacy had been demonstrated. The Kaplan-Meier curves of the cumulative proportion of patients with relapse during the double-blind treatment phase for Brexpiprazole (Rexulti™) and placebo groups are shown in Figure 6. The key secondary endpoint, the proportion of subjects who met the criteria for impending relapse, was

statistically significantly lower in Brexpiprazole (Rexulti™) treated patients compared with placebo group.

Figure 6: Kaplan Meier Estimation of Percent Impending Relapse in Study 5

Note: A total of 202 subjects were randomized. Among them, one placebo subject did not take investigational medicinal product and one Brexpiprazole (Rexulti™) subject did not have post-randomization efficacy evaluations. These two subjects were excluded from the efficacy analysis.

As Adjunctive Treatment of Major Depressive Disorder

The efficacy of Brexpiprazole (Rexulti™) in the adjunctive treatment of major depressive disorder (MDD) was evaluated in two 6-week, double-blind, placebo-controlled, fixed-dose trials of adult patients meeting DSM-IV-TR criteria for MDD, with or without symptoms of anxiety, who had an inadequate response to prior antidepressant therapy (1 to 3 courses) in the current episode and who had also demonstrated an inadequate response throughout the 8 weeks of prospective antidepressant treatment (with escitalopram, fluoxetine, paroxetine controlled-release, sertraline, duloxetine delayed release, or venlafaxine extended-release). Inadequate response during the prospective antidepressant treatment phase was defined as having persistent symptoms without substantial improvement throughout the course of treatment.

Patients in Study 228 (hereafter “Study 1”) were randomized to Brexpiprazole (Rexulti™) 2 mg once a day or placebo. Patients in Study 227 (hereafter “Study 2”) were randomized to Brexpiprazole

(Rexulti™) 1 or 3 mg once a day or placebo. For patients randomized to Brexpiprazole (Rexulti™), all patients initiated treatment at 0.5 mg once daily during Week 1. At Week 2, the Brexpiprazole (Rexulti™) dosage was increased to 1 mg in all treatment groups, and either maintained at 1 mg or increased to 2 mg or 3 mg once daily, based on treatment assignment, from Week 3 onwards. The dosages were then maintained for the 4 remaining weeks.

The primary endpoint was change from baseline to Week 6 in the Montgomery-Asberg Depression Rating Scale (MADRS), a 10-item clinician-related scale used to assess the degree of depressive symptomatology, with 0 representing no symptoms, and 60 representing worst symptoms.

At randomization, the mean MADRS total score was 27. In Studies 1 and 2, Brexpiprazole (Rexulti™) [+ antidepressant (ADT)] 2 mg/day and 3 mg/day were superior to placebo + ADT in reducing mean MADRS total scores. Results from the primary efficacy parameters for both fixed dose trials are shown below in Table 11. Figure 4 below shows the time course of response based on the primary efficacy measure (MADRS) in Study 1.

Table 11: Summary of Efficacy Results for Studies 1 and 2 for the Adjunctive Treatment of MDD

Study	Treatment Group	N	Primary Efficacy Measure: MADRS		
			Mean Baseline Score (SD)	LS Mean Change from Baseline (SE)	Placebo-subtracted Difference ^a (95% CI)
1	REXULTI (2 mg/day) +ADT*	175	26.9 (5.7)	-8.4 (0.6)	-3.2 (-4.9, -1.5)
	Placebo +ADT	178	27.3 (5.6)	-5.2 (0.6)	--
2	REXULTI (1 mg/day) +ADT	211	26.5 (5.6)	-7.6 (0.5)	-1.3 (-2.7, 0.1)
	REXULTI (3 mg/day) +ADT	213	26.5 (5.3)	-8.3 (0.5)	-2.0 (-3.4, -0.5)
	Placebo +ADT	203	26.5 (5.2)	-6.3 (0.5)	--

[figure not shown]
SD: standard deviation; SE: standard error; LS Mean: least-squares mean; CI: unadjusted confidence interval.

* Dosages statistically significantly superior to placebo.

^a Difference (drug minus placebo) in least-squares mean change from baseline.

An examination of population subgroups did not suggest differential response based on age, gender, race or choice of prospective antidepressant.

Figure 4: Change from Baseline in MADRS Total Score by Study Visit (Week) in Patients with MDD in Study 1

Dosage of Brexpiprazole (Rexulti™) Film-coated Tablet

For the treatment of schizophrenia, the recommended starting dosage for Brexpiprazole (Rexulti™) is 1 mg once daily on Days 1 to 4, taken orally with or without food. The recommended target Brexpiprazole (Rexulti™) dosage is 2 mg to 4 mg once daily. Titrate to 2 mg once daily on Day 5 through Day 7, then to 4 mg on Day 8 based on the patient's clinical response and tolerability. The maximum recommended daily dosage is 4 mg.

The recommended starting dosage for Brexpiprazole (Rexulti™) as adjunctive therapy for MDD is 0.5 mg or 1 mg once daily, taken orally with or without food. Titrate to 1 mg once daily, then up to the target dosage of 2 mg once daily. Dosage increases should occur at weekly intervals based on the patient's clinical response and tolerability. The maximum recommended daily dosage is 3 mg. It must be periodically reassess to determine the continued need and appropriate dosage for treatment.

For patients with moderate to severe hepatic impairment (Child-Pugh score ≥ 7), the maximum recommended dosage is 2 mg once daily for patients with MDD, and 3 mg once daily for patients with schizophrenia.

For patients with moderate, severe or end-stage renal impairment (creatinine clearance CL_{cr}<60 mL/minute), the maximum recommended dosage is 2 mg once daily for patients with MDD and 3 mg once daily for patients with schizophrenia.

Dosage adjustments are recommended in patients who are known cytochrome P450 (CYP) 2D6 poor metabolizers and in patients taking concomitant CYP3A4 inhibitors or CYP2D6 inhibitors or strong CYP3A4 inducers. If the coadministered drug is discontinued, adjust the Brexpiprazole (Rexulti™) dosage to its original level. If the coadministered CYP3A4 inducer is discontinued, reduce the Brexpiprazole (Rexulti™) dosage to the original level over 1 to 2 weeks.

Pharmacology of Brexpiprazole (Rexulti™) Film-coated Tablet

The mechanism of action of Brexpiprazole (Rexulti™) in the treatment of schizophrenia or adjunctive therapy of MDD is unknown. However, the efficacy of Brexpiprazole (Rexulti™) may be mediated through a combination of partial agonist activity at serotonin 5-HT_{1A} and dopamine D₂ receptors, and antagonist activity at serotonin 5-HT_{2A} receptors.

Brexpiprazole (Rexulti™) has affinity (expressed as K_i) for multiple monoaminergic receptors including serotonin 5-HT_{1A} (0.12 nM), 5-HT_{2A} (0.47 nM), 5-HT_{2B} (1.9 nM), 5-HT₇ (3.7 nM), dopamine D₂ (0.30 nM), D₃ (1.1 nM), and noradrenergic α_{1A} (3.8 nM), α_{1B} (0.17 nM), α_{1D} (2.6 nM), and α_{2C} (0.59 nM) receptors. Brexpiprazole (Rexulti™) acts as a partial agonist at the 5-HT_{1A}, D₂, and D₃ receptors and as an antagonist at 5-HT_{2A}, 5-HT_{2B}, 5-HT₇, α_{1A}, α_{1B}, α_{1D}, and α_{2C} receptors. Brexpiprazole (Rexulti™) also exhibits affinity for histamine H₁ receptor (19 nM) and for muscarinic M₁ receptor (67% inhibition at 10 μM).

Cardiac Electrophysiology

At 3-times the maximum recommended human dose (MRHD) for the treatment of schizophrenia and 4-times the MRHD for adjunctive therapy to antidepressants for the treatment of MDD, Brexpiprazole (Rexulti™) does not prolong the QTc interval to any clinically relevant extent.

Absorption

After a single dose administration of Brexpiprazole (Rexulti™) tablets, the peak plasma Brexpiprazole (Rexulti™) concentrations occurred within 4 hours after administration; and the absolute oral bioavailability was 95%. Brexpiprazole (Rexulti™) steady-state concentrations were attained within 10-12 days of dosing. Brexpiprazole (Rexulti™) can be administered with or without food. Administration of a 4 mg Brexpiprazole (Rexulti™) tablet with a standard high fat meal did not significantly affect the maximum concentration (C_{max}) or Area under the curve (AUC) of Brexpiprazole (Rexulti™). After single and multiple once daily dose administration, Brexpiprazole (Rexulti™) exposure (C_{max} and AUC) increased in proportion to the dose administered. *In vitro*

studies of Brexpiprazole (Rexulti™) did not indicate that Brexpiprazole (Rexulti™) is a substrate of efflux transporters such as multidrug resistance MDR1 (P-gp) and breast cancer resistance protein (BCRP).

Distribution

The volume of distribution of Brexpiprazole (Rexulti™) following intravenous administration is high (1.56±0.42 L/kg), indicating extravascular distribution. Brexpiprazole (Rexulti™) is highly protein bound in plasma (greater than 99%) to serum albumin and α 1-acid glycoprotein, and its protein binding is not affected by renal or hepatic impairment. Based on results of *in vitro* studies, Brexpiprazole (Rexulti™) protein binding is not affected by warfarin, diazepam, or digitoxin.

Elimination

Metabolism

Based on *in vitro* metabolism studies of Brexpiprazole (Rexulti™) using recombinant human cytochrome P450 (CYP1A1, 1A2, 2A6, 2B6, 2C8, 2C9, 2C19, 2D6, 2E1, and 3A4), the metabolism of Brexpiprazole (Rexulti™) was shown to be mainly mediated by CYP3A4 and CYP2D6. *In vivo* Brexpiprazole (Rexulti™) is metabolized primarily by CYP3A4 and CYP2D6 enzymes. After single- and multiple-dose administrations, Brexpiprazole (Rexulti™) and its major metabolite, DM-3411, were the predominant drug moieties in the systemic circulation. At steady-state, DM-3411 represented 23% to 48% of Brexpiprazole (Rexulti™) exposure (AUC) in plasma. DM-3411 is considered not to contribute to the therapeutic effects of Brexpiprazole (Rexulti™). Based on *in vitro* data, Brexpiprazole (Rexulti™) showed little to no inhibition of CYP450 isozymes.

Excretion

Following a single oral dose of [¹⁴C]-labeled Brexpiprazole (Rexulti™), approximately 25% and 46% of the administered radioactivity was recovered in the urine and feces, respectively. Less than 1% of unchanged Brexpiprazole (Rexulti™) was excreted in the urine and approximately 14% of the oral dose was recovered unchanged in the feces. Apparent oral clearance of a Brexpiprazole (Rexulti™) oral tablet after once daily administration is 19.8 (±11.4) mL/h/kg. After multiple once daily administration of Brexpiprazole (Rexulti™), the terminal elimination half-lives of Brexpiprazole (Rexulti™) and its major metabolite, DM-3411, were 91 hours and 86 hours, respectively.

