1. OBJECTIVE

The objective of this post marketing surveillance is to further gather local data on the safety and efficacy of Brexpiprazole (Rexulti™) Film-coated Tablet in the treatment of schizophrenia and adjunctive therapy of MDD.

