2. METHODS

2.1. DESIGN OF THE PMS

This is a post marketing surveillance of 8 weeks duration, on 300 male or female patients diagnosed to have schizophrenia and MDD in the Philippines.

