5. STATISTICAL ANALYSIS

Analysis of data will be limited to descriptive statistics only. Safety will be evaluated based on the reported AEs per assessment. Efficacy will be evaluated using the Clinical Global Impression-Severity (CGI-S) and Clinical Global Impression-Improvement (CGI-I) Scales to monitor severity and improvement from mean baseline score (before initial dose) up to the last assessment (Week 8 – Study Completion).

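### Does the active-control entry in the synopsis of a single-group study mean that the efficacy objective claims more than the design can show?

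*Protocol*

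**What the plan says.** The Study Design table in the synopsis has three relevant rows: "Blinding Open", "Control Active" and "Design Single Group". The synopsis also states "A total of 300 subjects will be included in the trial", and its test-product block lists brexpiprazole alone.

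The objective in the synopsis is "To provide post marketing surveillance data on the safety and efficacy of Brexpiprazole (Rexulti™) Film-coated Tablet for schizophrenia and adjunctive therapy of major depressive disorder". Section 1 puts it as to "further gather local data on the safety and efficacy of Brexpiprazole (Rexulti™) Film-coated Tablet", and the Introduction speaks of monitoring safety and efficacy.

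Section 2.1 says "This is a post marketing surveillance of 8 weeks duration, on 300 male or female patients". In Section 2.2, consent is sought for the administration of brexpiprazole and of no other study product.

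Reported adverse events are the primary outcome and the CGI scales are secondary. Section 5 says "Analysis of data will be limited to descriptive statistics only" and describes the efficacy summary as severity and improvement from baseline to Week 8.

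**The concern.** An active control and a single group cannot both describe this study unless a comparator is defined somewhere, and none is. The synopsis is where most readers look up a design. Someone who reads only the control row would expect adverse event rates and CGI results to have a concurrent reference.

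The worry then extends to the word efficacy. The study is open. The attending physician chooses whom to enrol and is responsible for the case report form that holds the CGI scores. The depression patients receive brexpiprazole on top of an antidepressant. An 8-week change from baseline therefore mixes any drug effect with natural course, regression to the mean, concomitant treatment and unblinded rating. The Introduction uses the same word, efficacy, for results of randomised, placebo-controlled trials. With an active control on the design table, a reader could take the CGI results as evidence of the same kind. If so, the protocol would promise something that its design cannot support.

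**Working it through.** The protocol gives no basis for the 300 patients (no power, effect size, rate or margin), so there is no figure to reproduce. The check has two parts: whether anything depends on the control entry, and what the earlier-trial figures can show.

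**1. Does anything use the entry?**

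| Element | Where | What it says | Needs a control? |
|---|---|---|---|
| Number of groups | Synopsis | Single group | No |
| Product | Synopsis; Section 2.2 | Brexpiprazole only | No |
| Sample size | Synopsis; Section 2.1 | 300 in total, no allocation | No |
| Objective | Synopsis; Introduction; Section 1 | Provide, monitor or gather data | No |
| Primary outcome | Synopsis; Section 4.1 | Reported adverse events | No |
| Efficacy outcome | Synopsis; Section 4.2 | Numbers and proportions by CGI score | No |
| Analysis | Section 5 | Descriptive; baseline to Week 8 | No |

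The protocol describes no comparator arms, no between-group comparisons and no hypothesis tests. The control row stands alone against everything else, including the row directly below it. No objective states superiority, non-inferiority or an effect against a reference.

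**2. What do the earlier trials show?** The ratio is the LS-mean change on placebo divided by the LS-mean change on brexpiprazole, from Tables 11 and 12 in the Introduction.

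| Trial and arm | Placebo / brexpiprazole | Ratio |
|---|---|---|
| Study 3, 2 mg (PANSS) | 12.0 / 20.7 | 0.58 |
| Study 3, 4 mg (PANSS) | 12.0 / 19.7 | 0.61 |
| Study 4, 2 mg (PANSS) | 13.5 / 16.6 | 0.81 |
| Study 4, 4 mg (PANSS) | 13.5 / 20.0 | 0.68 |
| Study 1, 2 mg (MADRS) | 5.2 / 8.4 | 0.62 |
| Study 2, 1 mg (MADRS) | 6.3 / 7.6 | 0.83 |
| Study 2, 3 mg (MADRS) | 6.3 / 8.3 | 0.76 |

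The two highest ratios come from arms whose confidence intervals for the difference from placebo include zero: (-7.2, 1.1) in Study 4 and (-2.7, 0.1) in Study 2. Without those arms, the ranges are 0.58 to 0.68 on PANSS and 0.62 to 0.76 on MADRS. Every ratio exceeds one half.

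Three limits apply. The ratios are for PANSS and MADRS at 6 weeks under blinding, not for CGI at 8 weeks in open practice. A blinded placebo arm is not an untreated course. The MADRS comparator was placebo plus an antidepressant. Above all, the ratios would be the same whatever the control row said, so they measure the limits of an uncontrolled design and not the consequence of the label.

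**The case for a change.** The strongest case for a change is that the protocol makes a false statement about whether the study is controlled, in its own design table, and that a few words would put it right. It is neither an extraction fault nor a matter left to an analysis plan. If the entry was meant to say that patients receive active drug, the control field is still the wrong place for it. The synopsis and Section 4.2 speak of evaluating the drug's efficacy, and the protocol nowhere warns that the word carries less weight here than in the trials it cites.

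The first part stands: the entry is wrong, and there is no reading that rescues it. The second part stands only as a caution for interpretation. Gathering and describing CGI outcomes under treatment is what Section 1 promises, and a single group can do that. The overclaim would have to be in the objective or the analysis, and neither contains a comparative or attributive statement. Replacing the word efficacy throughout would be a choice of terms and would correct no false figure or method. A remark that CGI change and adverse event rates have no concurrent comparator belongs naturally in the discussion of results in the study report.

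**Conclusion.** The control entry contradicts the design row beneath it and the rest of the protocol. It is a clerical slip. Someone amending the document for another reason could tidy the cell, but the plan does not need to change on this account: the number of patients, the data collected, the summaries and any decision drawn from them are the same with or without the correction.

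The step from the label to an overclaiming objective does not hold. The objectives are to supply and describe local data, safety is primary, and Section 5 confines the analysis to description of change within patients. The placebo-to-drug ratios of 0.58 to 0.83 are correct arithmetic and a fair reminder for whoever interprets the results. Carrying them over to CGI at 8 weeks is an assumption, and they say nothing about the mislabelled cell.

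This conclusion assumes that no comparator was intended. Everything outside that one row supports the assumption. If a comparator had been planned, its absence from the rest of the protocol would be a different and much larger matter.
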